 1.1 If you indicated that personal identifiers will be maintained for future research, provide the following information: a) How the information will be securely handled and stored b) assure confidentiality, and c) who will have access to the identifiers and/or codes

2.0 Describe any additional steps, if any, to be taken to assure that the subjects' identities and any personal identifying information are kept confidential.

ID: IRB#14-001827

View: NEW 10.1 - Study Summary - Research Study

Warning: Save your work at least every 15 minutes by clicking &Save or &Continue.

Study Summary - Research Study -

1.0 Study Materials: As applicable to this study, attach the following:

- Protocol, Dissertation Proposal or Study Plan
- Preliminary Data
- Surveys, Questionnaires or other instruments to be used with study participants
- References

Document Name	Document Version #
LMIL Tables and Figures.docx	0.01
LMIL Bibliography and References cited.docx	0.01
Levomilnacipran proposal 042014.docx	0.01

2.0 *Specific Aims: Indicate the purpose of the research, specifying the problems and/or hypotheses to be addressed.

Specific Aims and Hypotheses:

Primary Aim: To compare the efficacy and generate estimates of the effect sizes on primary and secondary outcomes between the treatment groups in a 12 week double-blind placebo controlled treatment trial with levomilnacipran compared to placebo. Hypothesis 1: We will observe detectable differences in primary (mood) and secondary outcomes (cognition, apathy and quality of life) between the two treatment groups favoring LMIL.

Aim 2: To test whether the two treatment conditions will show no difference in tolerability and safety. We will particularly focus on cardiovascular status (blood pressure, heart rate, ECG changes)

Hypothesis 2: There will not be a difference in the rate of adverse events between the two groups.

Exploratory Aim 3: To compare the patterns of functional and structural connectivity in the two intervention groups. Hypothesis 3: LMIL will lead to improved functional connectivity in brain network activity as measured with resting state (rs-) fMRI, and plasticity in brain macro- and micro-structure as measured with structural MRI and DTI compared to the PBO.

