Neuropsychological assessment (at baseline, at 12 weeks): Our approach to cognitive assessment and analyses is based on our prior work and benefits from input from [name]. We will use a focused test battery developed by [name], assessing domains which have shown impairment in geriatric depression, according to prior research by our group45 and others: 9,46-48 (1) cognitive control, which relates to mental flexibility and inhibition and adjustment of behavior; (2) verbal fluency, which requires strategic searching/organization of verbal knowledge; (3) episodic memory: including explicit memory for verbal and nonverbal information; and (4) information processing speed and attention, including an indices of complex and sustained attention. Most of the measures have 2 or 4 alternate forms that will be important in repeating them during follow up. In addition to the cognitive outcome measures, we will include a brief word reading test, the WAIS-IV Test of Premorbid Functioning (TOPF), a revision of the Wechsler Test of Adult Reading (WTAR),49 to estimate an individual premorbid cognitive functioning. We will conduct a confirmatory factor analysis to assess the goodness of fit of our a priori domain assignments. Finally, we will assess the validity of assignment to composite domains using confirmatory factor analysis. The tests variables derived from each and a priori composite domain assignment: Verbal Fluency (Category and Letter Fluency tests): Cognitive Control (Trailmaking test part B and Stroop Color-Word Interference test); Attention and Processing Speed (Trailmaking test part A; Stroop rapid color and word reading scores (averaged); Digit vigilance d-prime); and Episodic Memory (Rey Auditory Verbal Learning; Brief Visual Spatial Memory tests).

Safety evaluations. Physical examination and vital signs at baseline: pulse rate, systolic blood pressure, and body weight will be obtained at each visit, in addition to a 12-lead ECG at baseline, if any cardiac complaints are present. Laboratory tests (as listed below) will be performed at baseline. The UKU Side Effect Rating Scale,50 a comprehensive rating scale for monitoring adverse events of psychotropic drugs used in clinical trials, will be completed at all visits except screening.

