Randomization and treatment schedule: After all screening and baseline test results are reviewed and eligibility criteria are confirmed, medications will be dispensed if patients continue to meet eligibility criteria and sign the informed consent form. All eligible subjects will be randomized to levomilnacipran or placebo group using a computer-generated random assignment scheme, which assigned subjects in a 1:1 ratio to each group. Randomization will be done prior to subject s being assigned to the groups.

Follow up assessment: The follow up will take place weekly for the first four weeks of treatment, every two weeks for the remainder of the study. Each follow up assessment will include measures of efficacy and safety. The weekly frequency of contact with all subjects will serve as an additional safeguard to monitor worsening of depression, as well as the emergence of side-effects or suicidal ideations.

Study medications and treatment procedures. Subjects will be randomized to: 1) LMIL20-120 mg per day or 2) matching placebo. The allowed range of the drugs according to tolerability and efficacy assessments will be between 20-120 mg per day for LMILN. The dose finding procedures will be only performed in the first four weeks and after that will remain stable until the end of the acute trial, as it worked in our pilot study. We will assess the optimal dose of LMIL based on tolerability and safety in this population. The balance will be maintained between the efficacy and tolerability of medications. If symptoms worsen, the study drug will be tapered and discontinued. Subjects will be referred for clinical care at UCLA or the community. The PI will continue the observation for safety until the appointment is scheduled with the primary psychiatrist. The dose will be titrated according to the titration schedule, including if side-effects are mild or well tolerated and if CGI scores for improvement is 3 or higher. The titration rate is based on the currently recommended titration to achieve the greatest efficacy that may not work for geriatric patients. For that reason, we have safeguards against rapid titration with potential side-effects that will require a slower titration or staying at a lower dose.

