Hypothesis 1: The primary analyses will focus upon HAM-D24 scores and will be analyzed using general linear mixed model analysis (e.g., SAS PROC MIXED). The two treatment groups will be compared for time course of HAM-D-24 with the initial endpoint EOT at 12 weeks. Covariates may be included in the model as noted above. In addition, likelihood ratio ?2 comparison will examine group differences in remission (HAM-D24 =6) and response (HAM-D24 =10) at EOT. Analyses for the cognitive outcome variables will be akin to those described above for the continuous HAM-D scores. As noted in the Neuropsychological Assessment section, there are four cognitive domains that are being assessed. Of these, the two primary cognitive domains of interest for this proposal are Cognitive Control and Episodic Memory. A separate general linear mixed model as above will be estimated using these two domain scores as dependent variables. The remaining domains, namely Verbal Fluency and Information Processing/Attention will be examined as secondary outcome measures. Apathy will be examined using the AES total score and quality of life using SF-36 scores in similar mixed models.

Hypothesis 2: We will examine adverse events in the two treatment groups. A detailed comparison of the number as well as type of side-effects in the two treatment groups will be conducted using chi-square tests.

Hypothesis 3: LMIL will lead to improved functional connectivity in brain network activity as measured with resting state (rs-) fMRI, and plasticity in brain macro- and micro-structure as measured with structural MRI and DTI compared to the PBO. To address these hypothesis, summary MRI measures (e.g., substructure volume, diffusion metrics) will be included in the GLMMs as "covariates of interest." For whole brain or structure voxel-level or point based measures (e.g., thickness or activation), the GLMMs will be implemented in R (www. R.org). Time (of scan) will be treated as a continuous variable with random intercepts and slopes to account for within-subject correlations between repeated measurements to assess change and interactions amongst the interventions. Difference scores between baseline and 12-week follow-up may be substituted for some analyses. FDR and/or permutation methods will be used to control for multiple anatomic comparisons in whole-brain contexts.

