Hypothesis 4: The role of brain neuroimaging biomarkers in variability of treatment response is examined in this Hypothesis. Predictor variables: We predict that baseline measures of neuroimaging biomarkers of emotional responsivity; working memory and connectivity will be related to treatment outcomes. These predictions will be evaluated in the context of the models described above (i.e., general linear mixed model) by adding the posited prognostic variable as an additional predictor.

Power. With a significance level (alpha) of 0.05, 80% power, and N = 30 in each treatment arm, we can detect an effect size (ES, difference between group means as a multiple of the standard deviation) of 0.7. Using appropriate covariates such as age of onset, chronicity, and number of episodes can be expected to reduce variance and increase power for a given difference in mean, hence the two-sample power computations are conservative for this situation. This study will thus yield sufficient pilot data to justify conducting a larger study in the future.

Data management. Data management and analysis support will be provided by the UCLA SI-STAT services and [name] will supervise the data gathering duties of the study coordinator, including reviewing all data entry forms. 1. Randomization. The prestudy forms must be submitted before a patient can be randomized. A separate portion of the database will also be maintained for patients screened but not enrolled or randomized. Randomization schedules will be prepared in a masked manner by the statistician. 2. Data submission and quality control. Data forms will be delivered from the originating location to the central data unit within one week of being generated. When errors, omissions, or unclear information is detected on the paper forms, a copy

will be returned for corrections. The data manager will generate monthly reports summarizing missing and incorrect data will be sent to the PI. 3. Data confidentiality. Patient study forms will be stored in locked file cabinets and will be accessible only to authorized personnel. A shredder will be used to discard all unwanted study documents. Access to the data will be password protected with only authorized persons having knowledge of the password.

ID: IRB#14-001827

View: NEW 11.1 - Characteristics of the Study Population

Warning: Save your work at least every 15 minutes by clicking \$Save\$ or \$Continue.

Characteristics of the Study Population

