	information can be found in the attached protocol.	
	•	
2.0	*Provide your assurance that information about serious, unanticipated problems relate incidents and violations) will be reported to the IRB within the time frames specified by	
	Requirements.	
	Agree 🗹 🗹	
	Provide the following information as appropriate to the study:	
3.0	*Are there plans to perform an interim safety analysis?	
	● Yes ○ No	
	• 3.1	
	If yes, describe or indicate where the information can be	
	 found in the attached protocol. Adverse events produced by levomilnacipran may occur. All 	
	- //dverse events produced by leverininacipian may occur. An	

adverse events will be carefully monitored during each visit by using the UKU Side Effect Rating Scale. If any serious medical complication occurs, the PI may discontinue the study medication and may proceed with unblinding the treatment assignment or stopping treatment. We may discover undiagnosed mental and medical conditions in the process of the study, and we will ask for permission by means of a signed Permission to Use Personal Health Information form to report the results of the subjects examination to their primary physician or psychiatrist. An adjustment of the dose of their standing medications may be attempted once seen by their primary care physician. If no improvement occurs or if a prescription of a new medication is required, the study medications will be discontinued.

Discontinuation from the study will be considered if subjects experience:

a. Changes on ECG or in cardiac enzymes indicating cardiac ischemia or a new onset arrhythmia;

b. The development of any severe side-effects on the UKU Side Effect Rating scale rated as 3 or greater.

We will monitor blood pressure and pulse at every visit. We will repeat the ECG once during the trial to ensure safety. If any changes on ECG that signify ischemia occur, we will obtain additional tests of cardiac enzymes to rule out myocardial infarction (MI) (e.g., CK-MB; troponin).

All adverse events will be reported to the subjects and to their primary physicians and the UCLA IRB/ DSMB committee within 10 days of PI�s awareness.

- 1. If a patient demonstrates worsening of their symptoms or no response by week 8 or during follow up (i.e., CGI-I score >3) of treatment, they will be discontinued from the study and referred for appropriate clinical services.

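### Hypothesis 2 compares only the number and type of side-effects, so the graded UKU severity ratings do not enter the between-arm tolerability comparison

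*Combined protocol and SAP*

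**What the plan says.** All references are to the combined protocol and SAP.

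- **Aim** (section 10.1, item 2.0). Aim 2 is "To test whether the two treatment conditions will show no difference in tolerability and safety". The hypothesis beneath it is narrower: it predicts equal adverse event rates in the two arms.
- **Measurement** (section 10.1, item 4.0, Safety evaluations). The UKU Side Effect Rating Scale "will be completed at all visits except screening". Item 5.0 allows up to 10 visits, so up to 10 − 1 = 9 ratings per patient, if baseline is a separate visit from screening.
- **Use of severity during conduct** (section 15.2, items 3.1 and 4.1). Discontinuation is considered on "The development of any severe side-effects on the UKU Side Effect Rating scale rated as 3 or greater". Item 4.0 of section 10.1 also makes titration depend partly on whether side-effects are mild.
- **Analysis** (section 10.1, item 6.0, Hypothesis 2). "A detailed comparison of the number as well as type of side-effects in the two treatment groups will be conducted using chi-square tests".
- **Dropouts** (section 15.2, items 3.1 and 5.1). These are analysed by reason for termination, and side-effects are one of the reasons.

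No section specifies a between-arm comparison of UKU grade, worst severity, score or time course.

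**The concern.** Tolerability depends on how bad side-effects are as well as how many patients have them. If most patients in both arms report a symptom at some level, the drug could make it clearly worse while the counts stay alike. A comparison of number and type would not show this.

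The direction matters because the expected result is no difference. An analysis that leaves severity out makes that result easier to report. Item 4.0 also says the trial will judge the optimal dose on tolerability and safety in this population, so tolerability is one of the main things the pilot is meant to deliver. In item 6.0 the HAM-D24, cognitive, apathy and quality-of-life measures are all analysed as scores in mixed models. The UKU is rated repeatedly but is not.

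**Working it through.** **1. The plan's own figure.** The Power paragraph of item 6.0 reads "With a significance level (alpha) of 0.05, 80% power, and N = 30 in each treatment arm, we can detect an effect size" and defines it as the "difference between group means as a multiple of the standard deviation) of 0.7". Allocation is 1:1. Sidedness is not stated; two-sided is assumed here.

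Detectable difference = (1.960 + 0.842) × √(2/30) = 2.802 × 0.258 = 0.72, which rounds to the printed 0.7. At exactly 0.70 SD a two-sample t-test has 76% power with 30 per arm, and 71% with the 27 per arm left after the planned 10% attrition. This figure is for a difference in means. The plan states no power for Hypothesis 2.

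**2. Assumptions for the side-effect scenarios.** The documents give no side-effect rates by arm and no severity distribution. Their one contrast is in the background (item 3.0), where the commonest adverse events are said to occur about twice as often as on placebo. The following are therefore assumptions: a four-level grade (0 to 3), the placebo distributions, the severity mixes, and chi-square applied to any versus none. Chi-square power is by exact enumeration of two binomials. Power for the tie-corrected Wilcoxon test is from 200,000 simulated trials per scenario. All use 30 per arm and two-sided 0.05.

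**3. Drug shifts severity.** A latent normal severity is shifted by 0.7 SD, borrowed from the power paragraph. Drug rate of any side-effect = Φ(Φ⁻¹(p) + 0.7). For p = 0.80 this is Φ(0.842 + 0.7) = 0.94.

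| Placebo patients at grades 0/1/2/3 | Any: placebo → drug | Wilcoxon on grade | Chi-square on any/none |
|---|---|---|---|
| 70/18/9/3% | 30% → 57% | 63% | 57% |
| 50/30/15/5% | 50% → 76% | 68% | 54% |
| 30/35/25/10% | 70% → 89% | 70% | 45% |
| 20/40/30/10% | 80% → 94% | 70% | 38% |

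With 27 per arm the last row is 65% against 35%.

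**4. Severity changes, incidence does not.** With grades 20/50/20/10% on placebo and 20/20/35/25% on drug, Wilcoxon has 43% power and chi-square 5%, its error rate. Over three such patterns Wilcoxon runs from 15% to 78%; chi-square stays at about 5%.

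**5. Incidence doubles, severity mix unchanged.** The mix among those affected is 60/30/10% mild/moderate/severe in both arms. The last column instead makes all the extra events mild; the chi-square power is then unchanged.

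| Incidence | Chi-square | Wilcoxon, same mix | Wilcoxon, extra events all mild |
|---|---|---|---|
| 10% → 20% | 19% | 19% | 18% |
| 20% → 40% | 39% | 38% | 34% |
| 30% → 60% | 66% | 62% | 51% |
| 40% → 80% | 90% | 83% | 69% |

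**6. Reading the results.** Over the wider set of scenarios examined, the ordinal test runs from about 25 points below chi-square to about 72 points above it. The sign depends on what the drug does, which the documents do not say. Each test sees something the other can miss.

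**The case against.** The strongest reply is that Hypothesis 2 is about a rate, and a chi-square comparison of number and type is a proper test of a rate. This stands: the stated test is not wrong for the stated hypothesis. The gap is between that test and Aim 2, which also names tolerability.

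A reader might go further in three ways that the documents do not support.

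- **That severity is thrown away.** It is not. A high UKU rating prompts consideration of discontinuation, and dropouts are analysed by reason, so the severe end has an indirect route into the results. But that route covers only side-effects bad enough to end participation, and no comparison between arms is stated for it.
- **That the test loses a known amount of power.** The differences of about 6 to 32 points in step 3 come from one assumed model, a uniform shift in severity, which favours a rank test. Step 5 starts from the only contrast in the documents and shows no gain, or a loss.
- **That chi-square should be replaced, or a UKU total made the main tolerability endpoint.** Replacing it could lose power for a pure incidence effect. The documents describe no UKU total score, and a total would add unrelated symptoms together.

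The plan also does not say whether number means patients, events or events per patient, and a chi-square table can have more than two categories. Any versus none is therefore an interpretation. The main point does not rest on it, because none of these counts uses severity as the plan describes them.

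**Conclusion.** The point holds as an omission. Graded severity is collected repeatedly and acted on during the trial, but the between-arm comparison for Hypothesis 2 uses only number and type. A conclusion of no difference in tolerability would rest on incidence alone. This follows from the text and needs no assumption.

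The size of the effect on power is not known. It may be large, nil or negative, and every figure above rests on assumed rates, severity mixes and a four-level grade. The case for change rests on Aim 2 being only partly answered, not on a power figure. It is an inexpensive improvement, with the severity comparison placed beside the chi-square test.

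**What to change.** In item 6.0, Hypothesis 2:

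1. Keep the chi-square comparison of incidence and state what is counted.
2. Add one pre-specified between-arm comparison of severity: each patient's worst post-baseline UKU grade, by a Wilcoxon or proportional-odds test. Report the LMIL-placebo difference with a 95% confidence interval (for proportional odds, the common odds ratio), so that a finding of no difference is shown with its precision.
3. Optionally, as supportive analysis, put the UKU score in the mixed model already planned for HAM-D24, with the baseline UKU score as covariate.

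Cost: plan wording and a little more analysis, with no new data and no change to trial conduct. It adds one test in the tolerability domain, which the planned Simes correction within domains can cover. Any total score mixes unrelated symptoms, so the comparison by type of side-effect should stay beside it.

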Structural Imaging. Structural image analysis will incorporate: 1) volumetric and 2) tensor based morphometry (TBM) analysis methods. In brief, widely used Freesurfer http://surfer.nmr.mgh.harvard.edu/) processing streams that include segmentation of cortical and subcortical ROIs (with manual correction) will estimate regional tissue volumes for comparison across time and in association with clinical response. ROI segmentations will also be used for the connectivity analyses as described below. For whole brain analysis, TBM methods, shown as highly sensitive for detecting subtle changes in brain morphometry associated with maturation/aging or disease,68-74 will examine both global and local changes in brain tissue structure across treatment and time. In brief, TBM matches structures with similar intensity patterns, after which the gradients of the non-linear deformation fields required to inversely warp baseline to follow-up scans within subjects, and individual images to an anatomical minimal deformation target (MDT) across subjects are used to determine longitudinal and cross-sectional effects respectively at the voxellevel.68,71,75 Using general linear models (GLMs), discrete local volumetric changes in brain tissue structure may thus be determined across treatment groups, in association with clinical and cognitive measures, where rate of change in local tissue structure may be quantified.76 For example, we have applied TBM in 10 subjects with major depression scanned at baseline and after receiving six ECT treatments and 10 matched controls to show significant anterior cingulate volume reductions in patients vs. controls (Fig 5, top) and hippocampal volume expansions between baseline and the 6th ECT in patients (Fig 5, bottom), These structural changes demonstrate treatment-associated plasticity and confirm detection of treatment change over a relatively short period of time, (2-3 weeks).

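### Hypothesis 3 is a drug effect on MRI measures, but the only stated model role for summary MRI measures is as covariates, so the text is internally inconsistent and gives no explicit test for them

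*Combined protocol and SAP*

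**What the plan says.** Section 10.1, item 2.0 (Specific Aims) sets Exploratory Aim 3: "To compare the patterns of functional and structural connectivity in the two intervention groups". Hypothesis 3, given there and again in item 6.0, is directional and comparative: "LMIL will lead to improved functional connectivity in brain network activity as measured with resting state (rs-) fMRI", with structural and diffusion changes as well, all relative to placebo.

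Item 6.0 (Statistics and Data Analysis) then gives the method for Hypothesis 3. For summary measures it says that "summary MRI measures (e.g., substructure volume, diffusion metrics) will be included in the GLMMs as" covariates of interest. It names no dependent variable for these models. The mixed models described up to that point belong to Hypothesis 1: "The primary analyses will focus upon HAM-D24 scores and will be analyzed using general linear mixed model analysis", followed by similar models for cognitive domain scores, the AES total and the SF-36.

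The same paragraph continues with voxel-level and point-based measures. It then describes scan time as a continuous variable with random intercepts and slopes, using "repeated measurements to assess change and interactions amongst the interventions". It adds: "Difference scores between baseline and 12-week follow-up may be substituted for some analyses".

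The imaging text in item 4.0 plans some comparisons between arms. Under Structural Imaging, for tensor-based morphometry, "discrete local volumetric changes in brain tissue structure may thus be determined across treatment groups". Under Diffusion Imaging, advanced reconstruction methods are to be explored for differences between treatment groups. For the summary quantities the wording differs. Regional volumes are to be compared over time and related to clinical response. Diffusion metrics are to be examined over time and against clinical outcome and neuropsychological function. Network metrics are to be related to treatment response.

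**The concern.** Under Hypothesis 3 the treatment is the exposure and the MRI measure is the response. The sentence on summary measures puts the MRI measure on the other side of the equation. In that position its coefficient answers whether MRI and the model's outcome are associated given treatment, which is a different question.

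Two errors of interpretation could follow. A significant MRI term could be reported as support for Hypothesis 3 when the drug has done nothing to the brain measure. A real drug effect on the measure could go unseen because the measure is unrelated to mood. In addition, if a post-randomisation MRI value were entered in a mood model, the treatment coefficient in that model would be conditional on it and could no longer be read as the total treatment effect.

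The plan gives the study of neural mechanisms as its reason for preferring placebo to an active comparator, and it scans every participant twice, so the imaging contrast should be stated without ambiguity.

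**Working it through.** **The plan's own figure.** Item 6.0 (Power) gives a detectable effect of 0.7 SD with 30 per arm, alpha 0.05 and 80% power. The documents do not state sidedness; two-sided is assumed. Detectable effect = (1.960 + 0.842) × √(2/30) = 0.72, or 0.74 with the t distribution. This agrees with 0.7 to one decimal. The figure is generic and not specific to MRI. It serves below only as a plausible size for a drug effect.

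**Inputs.** From the documents: 1:1 allocation; 54 expected completers (item 4.0), so 54/2 = 27 per arm; scans at baseline and week 12. Assumed, with no source in the documents: the MRI-mood slope b (0.3 or 0.5), the direct drug effect on mood c (−0.35 SD), unit residual SDs, one change value per patient, and ordinary least squares in place of the mixed model.

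**Set-up.** T is treatment (0/1), M the MRI change and Y the mood change.

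- M = d·T + e₁
- Y = c·T − b·M + e₂

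Covariate reading: regress Y on T and M, and test M. The expected coefficient of M is −b. It does not contain d, so no value of the drug effect on MRI can move it.

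Outcome reading: regress M on T, and test T. The expected coefficient is d, which is the quantity in Hypothesis 3.

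**Results (27 per arm, 4,000 runs, two-sided 0.05):**

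| Drug effect on MRI, d | MRI-mood slope, b | MRI term significant in mood model | Treatment term significant with MRI as outcome |
|---|---|---|---|
| 0 | 0.3 | about 55% | about 5% |
| 0 | 0.5 | about 92% | about 5% |
| 0.7 | 0 | about 5% | about 72% |

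The Monte Carlo standard error is at most √(0.25/4000) = 0.8 percentage points. A direct t-test power calculation for 0.7 SD with 27 per arm gives 71%, in line with the last cell. A separate run with 30 per arm, 3,000 runs and b = 0.4 gave the same pattern: 84% against 4% with d = 0, and, with d = 0.7 and b = 0, 5% against 75%.

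**Effect on a mood model, if post-randomisation MRI is entered.** Without M the treatment coefficient is c − b·d. With d = 0.7 this is −0.35 − 0.3 × 0.7 = −0.56, or −0.35 − 0.5 × 0.7 = −0.70. With M in the model it becomes c = −0.35 in both cases. This is arithmetic on the chosen inputs; it shows the direction of the change, not a forecast of its size.

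**What the corrected analysis could detect.** With MRI change as the outcome, 80% power and no multiplicity correction: 0.72 SD (0.74 by t) with 30 per arm, and (1.960 + 0.842) × √(2/27) = 0.76 SD (0.78 by t) with 27 per arm.

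**The case against.** A reader might infer that the drug effect on MRI is never estimated, and that the summary measures are definitely to be placed in the mood models. The documents do not support either statement in that form.

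First, the sentence refers only to the GLMMs and names no outcome. That these are the mood, cognition, apathy and SF-36 models is the natural reading, because no other mixed models have been defined by then, but it remains an inference. Hypothesis 4, by contrast, refers back explicitly to the models already described.

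Second, the same paragraph describes repeated scans, interactions involving the interventions, and difference scores. These make sense mainly with MRI as the response and are not expressly confined to voxel-level data. Item 4.0 also plans voxel-level comparisons of local volume change between arms, describes resting-state fMRI as a means of examining treatment-related change, and proposes exploratory comparisons of structural connectivity between groups. Parts of Hypothesis 3 therefore do have a between-arm comparison.

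Third, the simulated percentages rest on assumed slopes and effects. The 55% and 92% are simply the power to detect an association that was put into the data.

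All of this stands, and it limits the point to summary measures. It does not remove the point. The later sentences name no summary measure as dependent variable and do not retract the covariate role, so the paragraph leaves the same variables with two incompatible roles. The simulation is needed only to show that the two roles give different answers, and the algebra shows that for any b and d.

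**Conclusion.** The Hypothesis 3 text in item 6.0 is internally inconsistent. The hypothesis is a between-arm effect on MRI measures. The one sentence that assigns a model role to summary MRI measures gives them a role that does not test it, and no sentence gives an explicit model with a summary measure as dependent variable and a treatment contrast.

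The percentages are illustrative, since every slope and effect size behind them is assumed. The structural result, that the covariate coefficient carries no information on the drug effect on MRI, needs only the linear model set out above. The shift in the mood treatment coefficient arises only if post-randomisation MRI is entered in a mood model, which the documents do not say will be done.

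The reach is limited. Aim 3 is labelled exploratory, the trial is a pilot, the Hypothesis 1 analysis is specified separately and does not depend on this sentence, and the voxel-level comparisons between arms are unaffected. What is at risk is the reading of the summary imaging results.

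**What to change.** Replace the sentence on covariates of interest under Hypothesis 3. State that each named summary MRI measure is the dependent variable, and that the contrast is the levomilnacipran minus placebo difference at 12 weeks. That contrast can come from a treatment-by-time term or from the change score adjusted for the baseline value. With only two scans per participant, the baseline-adjusted change score is the simpler choice.

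Then separate the other uses of MRI. Keep models with baseline MRI as a predictor of outcome under Hypothesis 4. Retain the planned analyses linking MRI change to clinical response and neuropsychological function, but label them as association analyses that are not tests of Hypothesis 3.

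The cost is a few sentences in item 6.0. The scans, the data and the software stay the same.
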